## 2. High Blood pressure

- If measured blood pressure is  $\geq 160/110$ , i.e. systolic blood pressure  $\geq 160$  mm Hg and/or diastolic blood pressure  $\geq 110$  mm Hg, study staff will call the participant's prenatal care provider immediately and have a plan in place before the patient is allowed to leave.
- If measured blood pressure is  $\geq 140/90$ , i.e. systolic blood pressure  $\geq 140$  mm Hg and/or diastolic blood pressure  $\geq 90$  mm Hg, study staff will instruct participants to contact their provider regarding the elevated measure to arrange appropriate follow-up. Additionally, study staff will notify the prenatal care provider by phone before the end of the study visit.
- At least one blood pressure reading must meet criteria when two readings are taken, and at least two blood pressure readings must meet criteria when three readings are taken.

## 3. Contraindications to moderate to high-intensity physical activity during pregnancy

If any of the following conditions are reported, study staff will notify the PI and interventionist(s) that the participant has developed a contraindication to moderate to high-intensity physical activity in pregnancy. The physical activity component(s) of the intervention may need to be modified. All moderate to high-intensity physical activity must be stopped and not resumed until after delivery. Participants may potentially continue low-intensity physical activity at the PI's discretion. The presence of any of the conditions below does not require a change in any dietary component(s) of the intervention. Participants for whom a change to the physical activity component(s) of the intervention is indicated should not be considered withdrawn from the study.

### Contraindications to moderate to high-intensity physical activity during pregnancy:

- Incompetent cervix/cerclage
- Persistent 2nd or 3rd trimester bleeding
- Placenta previa after 26 weeks' gestation
- Premature labor that requires hospitalization and treatment with medications to stop contractions
- Ruptured membranes
- Preeclampsia / gestational hypertension
- Severe anemia defined as a hemoglobin  $< 8$  or hematocrit  $< 24$
- IUGR defined as  $< 5$ th percentile with abnormal Umbilical Artery Doppler studies

## 4. High score on the Beck Depression Inventory II

- Actively suicidal
  - BDI-II question 9 value of 2 or 3 (regardless of BDI-II total score) requires notification of the Principal Investigator (PI) or a designated clinician with

appropriate training in mental health assessment. The research staff should wait with the patient until the PI or clinician has the opportunity to assess the participant. The PI or designated clinician should assess the patient for risk of imminent harm and contact emergency services if needed. If the PI or designated clinician is not immediately available, notify emergency services according to local standards. Research staff should wait with the participant until emergency services has assumed care. The participant's prenatal care provider should be informed within 2 business days.

- Severe depression
    - BDI-II score of 29-63 (and BDI-II question 9 value of 0 or 1) requires that research staff inform the participant about her elevated score and notify the PI or designated clinician who should assess the patient for safety and/or possible psychiatric referral. If the PI or designated clinician is not immediately available, the participant may leave unattended, but the PI/ designated clinician should contact the participant within 24 hours to assess her for risk of imminent harm and should contact emergency services if needed. The participant should be told to expect such contact from study personnel. The patient's prenatal care provider also should be informed within 2 business days.
  - Moderate depression
    - BDI-II score of 20-28 (and BDI-II question 9 value of 0 or 1) requires that the participant be informed and that it is recommended she see her physician for further evaluation. Sites may provide participants with materials on available mental health resources.
5. Incidental findings
- For imaging studies and all lab studies *except* the OGTT:** When incidental findings on imaging studies or out of range values on lab tests are obtained by study personnel, the participant will be notified and a copy of the report sent to her physician. For lab tests, this pertains only to those tests for which results are obtained in real-time.
- For study-collected OGTTs:** As often as possible, the OGTT's will be collected as part of routine care at the participants doctor's office, if this is not an option, and as a retention strategy, we will perform this assessment as part of the 24 week visit and share the results with the patient and doctor.
- No safety alert or action is required, for out of range values, when study OGTT results are obtained by review of results generated in the course of routine clinical care.
6. If study personnel suspect that an infant/child enrolled in the study is being abused or neglected they will notify the local child protective services office, law enforcement agency, or other local authority. This requirement applies to all sites, with or without a Certificate of Confidentiality.
7. Infant growth
- Infant length or weight-for-length assessed at the 12 month core visit that is at the 5th percentile or less according to the WHO growth standard requires that the mother be informed and that it is recommended that she have the infant seen by a health care provider for further evaluation.

- At the 6 week visit, infant growth *will* be plotted on the WHO growth chart. Length or weight-for-length at the 5th percentile or less at any visit, OR length or weight-for-length that has crossed two or more percentile lines downward, requires that the mother be informed and that it is recommended that she have the infant seen by a health care provider for further evaluation.

#### **4.6.1 Potential Risks**

The risks of phlebotomy include pain, a bruise at the point where the blood is taken, redness and swelling of the vein and infection. Risks from the questionnaires include discomfort and emotional upset. There could also be some minor pain or discomfort from a pinch from the calipers used for assessment of body fat.

The limitation of caloric intake and gestational weight gain has the potential to lead to weight loss during the pregnancy. The effects of weight loss in this population are unknown, but could increase the risk of fetal growth restrictions. Patients who loose in excess of 5% of their weight at the Baseline visit will have their diet reassessed to reassure adequate caloric intake.

#### **4.6.2 Definitions of Adverse Events (AE) /Serious Adverse Events (SAE)**

An **adverse event** is any untoward medical occurrence associated with participation in the study, including but limited to:

- Musculoskeletal injury that requires medical attention
- Fetal growth restriction (<5th percentile with abnormal umbilical artery Dopplers)
- Small for gestational age infant (birth weight <5th percentile)
- Unanticipated untoward medical events that are not plausibly pregnancy related and may be study related

A **serious adverse event** (SAE) is defined as an untoward medical occurrence, whether associated with study participation or not, that results in one of the following:

- Death
  - Maternal death
  - Fetal or infant death, including miscarriage, therapeutic abortion because of increasing signs of maternal or fetal compromise, and stillbirth.
- Life-threatening event
  - Life threatening events in the mother, fetus, neonate or infant are defined as those that in the view of the research staff and PI put the individual patient at imminent substantial risk of dying, or if continued participation in the study might have resulted in death.
- Hospitalization (initial or prolonged)
  - Maternal hospitalization or acute outpatient evaluation (e.g. in an emergency room or labor and delivery triage unit) alone is not sufficient to qualify as a serious adverse event. Hospitalization or acute outpatient evaluation for the following would not be considered a serious adverse event: term delivery, preterm premature rupture of membranes (pPROM), pyelonephritis, bedrest, contractions, ruling in or out preeclampsia, and preterm labor. \
  - Preterm delivery prior to 32 wks gestation is reported as a serious adverse event.
  - Any infant or child hospitalization after neonatal discharge and during the infant's participation in this trial is reported as a serious adverse event.
  - Any medical or surgical procedure performed (e.g., surgery, transfusion) itself is not the adverse event; instead, the condition that leads to the procedure is the adverse event.
- Disability or permanent damage

- If the adverse event resulted in a substantial disruption of the mother or infant's ability to conduct normal life functions, i.e., the adverse event resulted in a significant, persistent or permanent change, impairment, damage or disruption in the patient's body function/structure, physical activities and/or quality of life. The recommendation for bedrest does not constitute an SAE.
- Congenital anomaly /birth defect
- Medical Intervention to prevent permanent impairment or damage

Other serious important medical events also qualify. When an event does not fit the other outcomes, but may jeopardize the patient and may require medical or surgical intervention or treatment to prevent one of the other outcomes, this should also be reported as an SAE.

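### A non-serious adverse event counts only if it is associated with participation, a condition that can filter the named events unequally between arms

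*Combined protocol and SAP*

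**What the plan says.** Section 4.6.2 gives two definitions with different entry conditions.

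- **Adverse event:** "any untoward medical occurrence associated with participation in the study, including but limited to" four items. They are "Musculoskeletal injury that requires medical attention"; fetal growth restriction below the 5th percentile with abnormal umbilical artery Doppler findings; an infant with birth weight below the 5th percentile; and "Unanticipated untoward medical events that are not plausibly pregnancy related and may be study related".
- **Serious adverse event:** an untoward occurrence "whether associated with study participation or not, that results in one of the following", followed by the usual seriousness criteria and an open residual clause, "Other serious important medical events also qualify". For early birth the rule is "Preterm delivery prior to 32 wks gestation is reported as a serious adverse event".

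Section 4.6.1 foresees a harm from limiting calories and weight gain: "The effects of weight loss in this population are unknown, but could increase the risk of fetal growth restrictions". Section 4.6 appoints a Safety Officer, an obstetrician outside the study, to review adverse events within a week for a link to the protocol. Section 5.3 gives the DSMB all adverse events to date with a marker for new ones, and gives by treatment group only those outcome variables assessed mainly for safety. Sections 5.4 and 5.5 contain no adverse event analysis.

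**The concern.** A comparison of harms by arm needs the same rule for what counts as an event in each arm. Here the rule for non-serious events includes a causal judgement. A strained knee or a small infant is easy to link to participation for a woman on a calorie-limited diet and a walking programme. For a woman given websites, a pamphlet, general classes and newsletters, the same event has little to be linked to.

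The events at stake include those the protocol has most reason to watch. Growth restriction is the harm it anticipates from calorie limitation, and injury is the obvious harm of exercise. If the condition is applied literally, the non-serious table could show an excess in the intervention arm where there is none, or misstate a real one. The DSMB, which is left to set any stopping rule for harm, would see that table.

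**Working it through.** The plan states no adverse event rate, so there is no figure to reproduce. The check sets the sections side by side, followed by an illustration on assumed rates.

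**1. Is the condition deliberate and necessary?** The serious event definition, in the same section, drops it. Section 4.6 already gives the link to the protocol its own step, the Safety Officer's review. Relatedness can therefore be judged after an event is recorded, and the definition does not need to do it first.

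**2. Which events depend on the condition?**

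| Event | Subject to the condition as a named adverse event | Another route in both arms |
|---|---|---|
| Musculoskeletal injury | Yes | Hospitalization form (4.4.3), only if admitted |
| Fetal growth restriction with abnormal Doppler | Yes | Alert on activity contraindications (4.6, item 3) |
| SGA below 5th percentile | Yes | Derivable from birth weight (4.7.3) and gestational age at delivery (5.4.3) |
| Delivery at 32 to 36 weeks | Not named | Not serious under the preterm rule and not in 4.7; derivable from gestational age at delivery |
| Gestational diabetes, preeclampsia, cesarean, shoulder dystocia, neonatal hypoglycemia, NICU admission, birth trauma | No | Outcomes in 4.7.2 and 4.7.3 |
| Weight loss, blood pressure, depression, infant growth | No | Alerts at study visits (4.6) |

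Injury treated without admission has no other stated route. Growth restriction has an alert, but no tabulation of it is stated. SGA is recoverable.

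**3. Illustration.** Take 150 women per arm (section 5.2). Assume a true rate of 10% in both arms, with a share a of events accepted as associated with participation: a = 0.8 in the intervention arm and various values in control. The recorded rate is p = 0.10 × a and the expected count is 150 × p. The chance of a nominally significant difference at two-sided 0.05, by the normal approximation, is

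Φ{ [ |p1 − p2| − 1.96 √(2 p̄(1 − p̄)/150) ] / √( [p1(1 − p1) + p2(1 − p2)]/150 ) }, where p̄ is the mean of p1 and p2.

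For a = 0.5 in control: p1 = 0.08, p2 = 0.05, p̄ = 0.065. The two standard errors are 0.0285 and 0.0284, so (0.03 − 1.96 × 0.0285)/0.0284 = −0.91 and Φ = 0.18.

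| Share accepted, intervention / control | Expected recorded events | Chance of a false difference |
|---|---|---|
| 0.8 / 0.8 | 12 vs 12 | 5% (nominal) |
| 0.8 / 0.5 | 12 vs 7.5 | about 18% |
| 0.8 / 0.2 | 12 vs 3 | about 67% |
| 0.8 / 0.1 | 12 vs 1.5 | about 84% |

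The approximation is rough at the smallest counts. With equal true rates the recorded ratio is simply the ratio of the two accepted shares. The 10% rate and every share are assumptions; none is in the documents.

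**The case against.** The strongest reply is that the named items carry concrete criteria, so staff may record them as adverse events outright. A Safety Officer's search for a link would be redundant if every recorded event had already been judged linked, which suggests recording first and attribution second. Visit measurements are made by blinded staff (4.2, 4.7.5). No section says who applies the condition or that this person knows the arm. This stands as a reason to treat the bias as possible rather than established. It does not settle the matter, because the text does not say that listed items count regardless. The Study Coordinator is unblinded, and no section provides for masked attribution.

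A reader might also infer more than the documents support:

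- **That the list is closed at four items.** A definition beginning with any occurrence and ending in a residual item does not fit a closed list. A dropped *not* is far more likely.
- **That pregnancy harms below the serious threshold go unseen.** Many are outcomes, alerts or hospitalization-form items in both arms.
- **That the DSMB cannot compare SGA.** It can be derived from data already collected, and section 5.3 sends safety outcome variables by group.
- **That the apparent risk of SGA would at least double.** That needs an assumed event rate and assumed attribution shares.
- **That the pregnancy-related exclusion in the residual item must go.** With so many pregnancy events collected elsewhere, keeping it is a defensible division of work.

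**Conclusion.** The point holds for non-serious adverse events only. The definition makes association with participation a condition of being counted, and the two arms differ in how readily that condition can be met. Counts of injury, growth restriction and SGA taken from adverse event forms are therefore not a dependable comparison by arm. Injury not leading to admission is the most exposed, and SGA the least. Separately, delivery at 32 to 36 weeks has no named place in the safety definitions or in 4.7, and no adverse event table by arm is specified.

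The size of the distortion cannot be derived from the documents. It is nil if staff record the listed items regardless of attribution or attribute equally in both arms, and grows as control attribution falls. The conclusion rests on the definition being followed as written. It does not touch the primary weight-gain analysis, serious adverse events, the 4.7 outcomes, safety alerts or hospitalization forms.

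**What to change.** 1. In 4.6.2, state that the listed events are adverse events in either arm regardless of attribution, matching the serious event definition.
2. Insert the missing *not* before *limited* in the opening sentence.
3. Record relatedness as a separate field at the Safety Officer review already planned in 4.6, masked to arm where feasible. For an exercise injury, the description may reveal the arm.
4. In 5.3 and 5.4, specify tables by arm of musculoskeletal injury, fetal growth restriction, SGA below the 5th percentile and delivery before 37 weeks, for the DSMB and the final report. Derive SGA and preterm delivery from birth weight and gestational age at delivery rather than from adverse event forms.

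The cost is revised wording and some additional adverse event forms, with no new visits or procedures. Under 7.2.2 the consortium's Safety Committee sets common definitions, so the change needs its agreement to keep the trials harmonized.

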#### ***4.6.3 Surveillance and Reporting Procedures***

Serious adverse events should be telephoned, faxed, or emailed within 24 hours of ascertainment by the center PI or study coordinator to the NIDDK program official. Because a written record of notification is required, telephone notifications must be followed with written documentation that the NIDDK has been informed. The NIDDK program official will immediately share reports with the DSMB chairperson. Together they will decide if the entire DSMB should be notified in real time or if the report can be reviewed as part of the cumulative safety reports at the next semi-annual meeting of the DSMB. The initial notification should be followed by a written adverse event form completed by the PI at the reporting center and forwarded to the NIDDK and the RCU within 3 days of ascertainment of the event. The RCU will inform the Data and Safety Monitoring Board of adverse events experienced by study participants in the semi-annual meeting reports.

#### ***4.6.4 Safety Monitoring Plan***

Participants with elevated depressive symptoms will be informed of the possibility that they are depressed and referred to their OBGYN or a mental health provider for further evaluation and treatment. If a participant reports suicide intent, she will be evaluated immediately and appropriate intervention initiated (e.g., staff accompany subject to the emergency room, immediate psychiatric consultation). After the depression has been evaluated and treated, a determination about the safety of continued participation in the study will be made. The OBGYN and any mental health professional involved in the participant's care should help with this determination.

#### ***4.6.5 Rules for Participant Termination***

Participants may withdraw from the study at any time. Permission will be sought to continue to collect outcome data for use in the analysis. Patients who incur a pregnancy loss after randomization or preterm delivery will also be included in the analysis, with the last weight obtained at a study visit or a clinical visit used for the primary outcome.

### ***4.7 Study Outcome Measures and Ascertainment***

#### ***4.7.1 Primary Outcome***

The primary outcome is GWG as assessed continuously by the difference between the maternal weight measured at the 36 week visit and the baseline visit.

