**TABLE 3: Data Collection Visits for Both Groups**

Measures	VISITS							
	Screening 8- 15.3 wks	Prenatal				Postpartum		
		Baseline 9-15.4 wks	Random- ization 9-15.6wks	24-28 weeks*	35-37 wks	Delivery	6 weeks	12 months
Visit Location	OB Office	DPM Clinic	DPM Clinic	DPM Clinic	DPM Clinic	Prentice Hospital	DPM Clinic	DPM Clinic
Consent	x	x						
Self-reported pregravid weight	x							
Height (Mom)		x						
Weight (Mom)		x		x	x		x	x
Blood pressure		x		x	x		x	x
Waist and Hip circumference							x	x
Blood: 8 Hr Fast for storage (glucose, insulin, CRP, IL-6 and adiponectin, lipid panel, vitamin D and metabolomics)		x		(routine; OGTT at OB visit)***	x		x	x
HbA1c		x					x	x
Spot Urine		x		x	x		x	x
First Diet recall (ASA 24)		x			x		x	x
Second diet recall (ASA24)*			x		x		x	x
Actigraph		x	Returned		x		x	x
Cord blood collection						x		
Weight (Baby)						x	x	x
Length (Baby)						x	x	x
Skinfold , baby						x		x
Head circumference						x		
PEA POD						X		
BodPod (Mom)							x	x

Breastmilk (as relevant)							x	x
Sleep/Stress Behavioral Data Collection **		x		x	x		x	x
Infant feeding & activity					X		x	X
Blood: Infant, at 12 months as consented								X
Infant stool sample, as consented						x	x	x

\*Two 24 Hour recalls will be completed. The first is completed at the clinic for 4 of the 5 clinic visits (not 24-28 wks), The second recall will be completed within 2 weeks of the first one.

\*\* Detailed survey data collection listed below in Table 4 (see below).

\*\*\*2hr OGTT collected at DPM clinic is not ordered at routine OB visit

As part of the LIFE Moms Steering Committee the following blood collection amounts have been established.

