(diffusion editing) and the low molecular weight components (Carr-Purcell-Meiboom-Gill pulse sequence) respectively. Ultra-performance liquid chromatography (UPLC)-MS profiling will be used in general screening mode using in-house methods [50]. Targeted analysis will be conducted for alkylresorcinols (fibre), prolinebetaine (citrus fruit) and S-methyl-L-cysteine sulphoxide (cruciferous vegetables) using a combination of UPLC-MS and NMR methods. Data will be analyzed using multivariate statistical tools including linear projection methods and cluster analyses in order to identify candidate metabolic biomarkers associated with obesity or intervention. Candidate metabolic biomarkers of obesity in pregnant mothers at baseline and 36 weeks will be identified using available databases, by further analytical experiments such as 2-dimensional NMR pulse sequences including homo and heteronuclear correlation spectroscopy, LC-NMR-MS etc and by statistical correlation spectroscopy methods [48]. Several mathematical strategies will be applied to achieve higher sensitivity in detecting panels of inter-related biomarker candidates associated with maternal weight gain, maternal BMI and infant birthweight and adiposity. These methods will accommodate the specific challenges posed by spectral data including low sample:variable ratio, colinearity of predictor variables, confounding factors or co-morbidities correlated with both predictor and outcome variables etc. A flexible framework based on generalized linear models will be implemented to identify univariate and multivariate relationships of predictor variables with outcomes while statistically accounting for potential confounding effects observed in human studies. The choice of a model will be considered based on the probability distribution of a clinical outcome and both Bayesian and conventional maximum likelihood inferences will be made.

In addition to the ASA24 nutrient data, diet quality differences will be measured by metabolomic assays specifically related to fruit/vegetable and dietary fiber intake as alkylresorcinols (fiber), prolinebetaine (citrus fruit) and S-methyl-L-cysteine sulphoxide (cruciferous vegetables) in maternal urine and cord blood.

**Weight** will be measured without shoes, wearing light clothing on a calibrated beam balance scale at the Baseline visit, and at 24-28 week, and 35-37 weeks prenatal visits and the 6 week and 12 month postpartum visits.

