### ***4.5 Patient Management and Follow-up***

The Study Coordinator will continually be in touch with all participants in both groups. Scheduling of data collection visits will be an ongoing process with reminder calls/texts prior to each scheduled visit.

Participants in the Lifestyle Change group will further be followed by the nutritionist who will interact in person during individual and group sessions. In addition the Study coaches will be in touch weekly through electronic self-monitoring with feedback dialogue.

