### ***5.4 Analysis Plan***

All statistical analyses will be based upon the total cohort of patients randomized into the trial. Although data on some patients may be missing, all relevant data available from each patient will be employed in the analyses. Patients will be included in the treatment group to which they were randomly assigned regardless of the adherence to the intervention.

The primary analysis will consist of a simple comparison of GWG using an independent t-test. While this is a longitudinal study, and taking advantage of second trimester weights would be a more powerful analysis, there is currently no indication that the pattern of weight gain (whether excess weight gain occurs in the second trimester or third) is associated with worse outcomes. As the intent of this trial is to limit GWG, the analysis is designed to specifically address the comparison of mean weight gain in the two groups. Mean and standard deviation of weight gain will be reported. If the groups are found to differ on a pre-treatment factor known to be a factor related to weight gain, the statistical analysis will adjust for these differences using a multiple linear regression model. Additionally, adjusted means and confidence intervals will be presented after adjusting for factors such as age, pre-pregnancy BMI, and race.

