### ***5.4.3 Handling Missing or Incomplete Data***

Every effort will be made to minimize missing or incomplete data. Due to the nature of the study, there will be incomplete data that will be needed to address via statistical modeling. Specifically, we do not expect linear imputation to adequately address missing GWG for women who experience pre-term labor. In these cases, we will examine sensitivity to several assumptions via multiple imputation methods which will include weight gain at 24-28 weeks and through delivery, pregnancy complications and gestational age at delivery.

The first strategy will be to prevent the occurrence of missing outcome data. Missing pregnancy outcome data (including maternal weight gain) as well as missing neonatal outcomes derived from the medical charts are expected to be very low. Women who plan to deliver at a hospital outside of the study center will be excluded before randomization. All women will be required to sign a medical records release for themselves and their newborn prior to randomization in case delivery does occur elsewhere. Multiple methods for contacting women will be sought at the initial interviews, including contact information for friends and relatives. Loss to follow up and missing and incomplete data will be monitored closely by the Design, Data Quality and Data Analysis Committee of the Consortium, as well as the DSMB, to solve potential issues of missing data before there is a substantial impact on the results.

For data collected as responses to questionnaires, all forms will be reviewed for completeness before the participant leaves the study visit. Data entry will be accomplished quickly so that missing values may still be retrieved. For weight gain and related outcome variables in particular, if the study measured weight from the scheduled third trimester study visit at 35-36 weeks is not available, the closest maternity care provider visit weight (preferably on or before 36 weeks) will be used. This last weight will be corrected for length of gestation. If a loss occurs after randomization but before any further weight measurements are performed, a value of zero will be used for the primary outcome.

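### Primary weight gain is a raw difference over an interval of varying length, and only substitute weights are corrected for gestation, to a week the plan does not state

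*Combined protocol and SAP*

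**What the plan says.** Section 4.7.1 takes the primary outcome as the "difference between the maternal weight measured at the 36 week visit and the baseline visit"; section 3.1 says the same. Section 5.4 states: "The primary analysis will consist of a simple comparison of GWG using an independent t-test".

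**Timing of the two weights.** Table 3 heads the first weighing "Baseline 9-15.4 wks". I read 15.4 as 15 weeks 4 days, because the neighbouring randomisation column ends at 15.6 and section 3.4.2 sets that limit at 15 weeks 6 days. Table 3 puts the late visit at 35-37 weeks, and the weight paragraph of section 4.4.3 agrees ("35-37 weeks prenatal visits"). Section 5.4.3 instead refers to a "scheduled third trimester study visit at 35-36 weeks is not available". The diet and activity paragraphs of section 4.4.3 use 36-38 weeks for their late-pregnancy measures.

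**Correction for gestation.** If the study weight is missing, section 5.4.3 substitutes the nearest provider weight and adds: "This last weight will be corrected for length of gestation". Section 5.4.4 adjusts the last weight for gestational age after withdrawal before 36 weeks, and treats pregnancy loss and preterm delivery similarly. Section 4.6.5 also uses the last weight after loss or preterm delivery but mentions no correction. No section gives a method or a target week, and none corrects a weight taken at the scheduled visit.

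**Adjustment.** Section 5.4 adjusts by regression "If the groups are found to differ on a pre-treatment factor known to be a factor related to weight gain". Section 5.5 rules out adjusting for gestational age at delivery and does not mention gestational age at weighing.

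**The concern.** By correcting substitute weights, the plan accepts that the week of weighing affects measured gain. It then leaves most weights uncorrected. A scheduled weight at 35 weeks enters as measured, while a provider weight at the same week is corrected to an unnamed week. Two analysts following the text could build different primary variables.

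The two sources of timing variation need separate treatment. Gestational age at Baseline is fixed before randomisation, so it adds noise but no expected bias. Gestational age at the late visit arises after randomisation. The t-test has no term for it, and the conditional adjustment in section 5.4 is limited to pre-treatment factors. If the arms attended at different average gestational ages, the difference in gain due to timing would be reported as part of the treatment effect.

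**Working it through.** **Inputs from the documents.** SD 15 lb, target difference 5 lb, 143 women per group, two-sided alpha 0.05, 80% power (section 5.2); visit windows (Table 3).

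**Assumption.** The documents give no rate of gain near 36 weeks. I use 0.4 to 1.1 lb/week throughout.

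**1. The plan's sample size.** The exact two-sample t-test for 5 lb with SD 15 lb needs 142.2 per group, so 143; power at 143 is 80.2%. The stated figure is reproduced.

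**2. Interval between the weights.**
- Shortest: 35w0d − 15w4d = 19.4 weeks.
- Longest: 37w0d − 9w0d = 28.0 weeks, or 28.9 if the window runs through 37w6d.
- Width due to Baseline timing: 15w4d − 9w0d = 6.6 weeks. Width due to late-visit timing: 2.0 weeks (2.9 on the wider reading).

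Most of the spread therefore precedes randomisation.

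**3. Noise.** With timing uniform in each window, variance in weeks² is width²/12. Share of outcome variance = rate² × width²/12 ÷ 15².
- Baseline timing: 6.571²/12 = 3.60. At 0.4 lb/week, 0.16 × 3.60/225 = 0.26%. At 1.1 lb/week, 1.21 × 3.60/225 = 1.94%.
- Both windows together, on the wider late reading: 0.3% to 2.3%. Removing all of it lowers the SD to 14.98-14.83 lb and raises power at 143 per group from 80.2% to 80.3-81.1%.

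**4. Bias if late-visit timing differed by arm.** SE = 15 × √(2/143) = 1.77 lb. Bias b = rate × difference in mean timing. Type I error = 1 − Φ(1.96 − b/SE) + Φ(−1.96 − b/SE).

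| Arm difference in mean timing | Bias (lb) | Share of 5 lb | Type I error |
|---|---|---|---|
| 0.25 week | 0.10-0.28 | 2-6% | 5.0-5.3% |
| 0.5 week | 0.20-0.55 | 4-11% | 5.2-6.1% |
| 1 week | 0.4-1.1 | 8-22% | 5.6-9.5% |

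Chance alone would not produce such differences: with uniform timing, the SE of the arm difference in mean timing is 0.07-0.10 week. A systematic cause would be needed.

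**5. Mixed handling for one woman.** Take a weight at 35w0d. From the scheduled visit it is used as it stands. From a provider, and if the unstated target were 36w0d, it would rise by 1 × 0.4 to 1.1 = 0.4-1.1 lb. If the target were 37w0d, it would rise by 0.8-2.2 lb. The documents do not say how many women will need a substitute weight, so the effect on the arm means cannot be calculated.

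**The case against.** The strongest reply is that nothing in the plan predicts an arm difference in visit timing. A reader might infer one from section 4.5, where for the intervention arm "the Study coaches will be in touch weekly through electronic self-monitoring with feedback dialogue". The same section says that the Study Coordinator keeps in touch with both groups and that visits are scheduled with reminders, without distinction by arm. Coach contact is intervention content, not visit scheduling. The coordinator is unblinded, but the staff who take the measurements are blinded. This reply stands: the bias is a possibility that the analysis leaves open, not an expected one.

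A reader might also take the whole 19-to-29-week spread as a source of bias. It is not: 6.6 weeks of it is Baseline timing, which randomisation balances in expectation, and section 5.4 could adjust for it as a pre-treatment factor. The noise is also small.

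Finally, correcting off-schedule weights can be read as an attempt to bring them into line with the scheduled visit. That is a fair account of the intent. Without a reference week or method, though, the intent cannot be carried out reproducibly, and two stated windows for the scheduled visit leave unclear what the substitutes should be aligned to. The mixed models in section 5.4.1 explore patterns of gain and do not define the primary variable.

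**Conclusion.** The firm part needs no assumption. The primary variable mixes corrected and uncorrected gains, the correction has no method or target week, and the late window for weight is given two ways.

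The bias is conditional and modest. A half-week arm difference at 0.4-1.1 lb/week would move the estimate by 0.2-0.55 lb and give a type I error of 5.2-6.1%. A reader might infer a type I error of 8-9%. That needs a full-week difference in arm means, half of the printed two-week window, with gain of about 1 lb/week (b = 1.0 lb gives 8.7%), and the documents offer no basis for expecting it. Baseline timing costs at most about 2% of variance.

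These sizes rest on the assumed weekly rate, uniform timing within the windows (for the noise), and the plan's SD of 15 lb with 143 per group. The point merits a clarification, one covariate and one sensitivity analysis. It does not put the primary comparison in doubt.

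**What to change.** 1. Pre-specify gestational age at the Baseline weight, from the project gestational age of section 3.4.3, as a covariate in the GWG model, so that its use does not depend on an observed imbalance.
2. State one late-visit window, reconciling Table 3 and section 4.4.3 with section 5.4.3, and one reference gestational age. Write down the correction method. Pre-specify a sensitivity analysis that brings every late weight, scheduled or substitute, to that reference by the same method.
3. Report gestational age at both weigh-ins by arm, so that readers can see whether timing differed.

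Do not enter gestational age at the late weighing as a covariate in the primary model: it is a post-randomisation variable. The changes do not conflict with section 5.5, which concerns gestational age at delivery only.

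The cost is a few sentences, one covariate and one extra model; no new measurements are needed. The downside is that the sensitivity analysis rests on an assumed rate of gain near 36 weeks, so that rate should be stated and varied. The sample size is essentially unaffected.
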